### Protocol Summary

Full Title:	A Randomized Controlled Trial Comparing Low Doses Of Aspirin In The Prevention Of Preeclampsia (ASAPP)
Short Title:	ASAPP
Clinical Phase:	III
Principal Investigator:	[name]
Sample Size:	N= 400 which may be modified after the first stage of our study
Accrual Ceiling:	400
Study Population:	Pregnant women < 16 weeks of gestation at high risk of PE (preeclampsia in a prior pregnancy, multifetal gestation, chronic hypertension, Type 1 or 2 diabetes, renal disease, autoimmune disease).
Accrual Period:	5 years
Study Design:	Open-label, randomized clinical trial. First stage: pilot to determine feasibility and sample size and second stage: completing the clinical trial
Study Duration:	9 months for each patient (from recruitment until 6 weeks postpartum)
Intervention Description:	Randomized to 81mg vs. 162mg of aspirin per day
Primary Objectives:	To compare the incidence of preterm PE and PE with severe features in women treated with 81mg to those treated with 162mg of aspirin per day.
Secondary Objectives:	

Evaluate and compare the adherence of pregnant women to 81 mg and 162 mg of daily low-dose aspirin using a validated, Simplified Medication Adherence Questionnaire (SMAQ).

Compare maternal and fetal outcomes in pregnant women at a high risk for preeclampsia who are treated with either 81 mg or 162 mg of daily aspirin during pregnancy, including preeclampsia <math>\geq</math> 37 weeks, severe maternal hypertension, preterm delivery, fetal growth restriction, placental abruption and maternal/fetal mortality.

To compare the time-to-event for developing PE for women treated with 81mg vs. 162mg of aspirin per day.

To assess the adherence to low dose aspirin in pregnant women that are a high risk for preeclampsia and compare adherence rates for women on 81mg vs 162mg of aspirin per day.

Exploratory Objectives:	To assess the impact of specific co-morbidities (diabetes, chronic hypertension, renal disease and autoimmune disease), blood pressure

*control, age and race on the relationship between treatment group and PE incidence.*

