## **12.3 Sample Size/Accrual Rate**

A sample size of 394 participants (197 for each group) will allow us to detect at 7.1% difference in the incidence of PE between the 2 groups. This is based on prior data reporting an incidence of PE of 8.6% and 1.5% for 81mg and 150mg of ASA respectively (10, 12) with a target 85% power and a Type 1 error rate (alpha) of 5% (two-tailed). Assuming a response rate of 50%, we will aim to screen 788 women.

The above calculation is however only theoretical and very approximate. The incidence of PE in women on 162mg of ASA is not known and the incidence of PE in the 81mg of daily ASA that has been reported in the above-mentioned literature (10) appears to be far below the incidence of PE of 33.6% in

our patient population (16). Our elevated rate of PE likely stems from referral bias and from the fact that, at the time of this study, aspirin was still not widely prescribed as it was not standard of care yet.

The study will therefore be done in two stages:

Stage 1: Pilot stage to assess feasibility and ensure feasibility and safety with the randomization of 50-100 patients. The incidence of PE in the 2 groups will be evaluated and serve to calculate a sample size with a power of 85% to detect the observed difference between the two groups (adjusting for the interim analysis effect).

We will recruit 50-100 patients in the initial stage of this trial. We have obtained an approximate estimation for the number of patients we see in the Women's Health Practice and in J130 that would meet eligibility criteria for our study at <16 weeks gestation with USPTF high risk factors for the development of pre-eclampsia. We have sampled 3 separate months of the year so as to account for holidays, change in faculty coverage, and seasonality. In the month of January, there were 9 eligible patients; in October, there were 32 eligible patients; and in June, there were 29 eligible patients. Given the variability from month to month, and assuming a 50% response rate, 11 patients a month could potentially be randomized. Assuming a 75% adherence rate, we anticipate having approximately 50 patients for initial assessment of feasibility and safety by the end of 6-12 months, after which we would perform a more accurate power analysis and continue with the second stage of our study.

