#### **12.5 Analysis of Secondary Endpoints**

Standard descriptive statistics (such as mean or median, range and percentage) will be computed for patient characteristics. Baseline characteristics will be compared across treatment arms using Mann-Whitney U (for non-parametric variables), student's t-test (for normally distributed variables) or Chi-square tests (for categorical variables). Group differences in the incidence of preterm PE (<37 weeks) and PE with severe features (our primary outcome) will be tested using Chi-square.

As secondary analyses, multivariate logistic regression will be used to further assess the impact of co-morbidities (diabetes, chronic hypertension, renal disease and autoimmune disease), blood pressure, age and race on the relationship between treatment group and PE incidence. An exploratory analysis will be made to compare the time-to-event for PE across the 2 treatment groups using a log-rank test and a cox-regression model to adjust for the above-mentioned possible confounders. We will use Stata 15 (StataCorp. College Station, TX) for data analysis.

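### If PE events fall near the 20 or so the trial is sized on, the adjusted logistic and Cox models in section 12.5 are fragile under ordinary maximum likelihood; a penalised fit should be pre-specified

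*Combined protocol and SAP*

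**What the plan says.** Section 12.5 tests the primary outcome with an unadjusted Chi-square test. As secondary analysis, "multivariate logistic regression will be used to further assess the impact of co-morbidities (diabetes, chronic hypertension, renal disease and autoimmune disease"), and the list goes on to blood pressure, age and race. As exploratory analysis it compares time to PE with a log-rank test and "a cox-regression model to adjust for the above-mentioned possible confounders". The software is Stata 15. The section does not mention penalised or exact estimation, a limit on the number of terms, the coding of race and blood pressure, or what to do if a term cannot be estimated. I therefore read it as the default maximum-likelihood and partial-likelihood fits.

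Section 12.3 gives the planning figures: "A sample size of 394 participants (197 for each group"), "an incidence of PE of 8.6% and 1.5% for 81mg and 150mg of ASA respectively", with a "target 85% power and a Type 1 error rate (alpha) of 5% (two-tailed"). It adds that "The above calculation is however only theoretical and very approximate", reports 33.6% PE in the centre's own population, and recalculates the sample size after a pilot stage. The Protocol Summary gives the size as "N= 400 which may be modified after the first stage of our study".

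**The concern.** The number of terms in the adjusted models was set without reference to the number of PE events they will rest on. At the planning rates there are very few events per coefficient, and almost all of them fall in one arm. Three things can then go wrong with an ordinary fit.

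- A small risk group, such as renal or autoimmune disease, may contain no PE event, and its coefficient then has no finite estimate.
- If no woman on 162 mg develops PE, the treatment odds ratio is estimated as 0 and its logarithm is not finite.
- Where the fit does converge, the estimated effect tends to lie too far from no effect.

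These models give the only adjusted estimates of the dose effect in the plan, and the logistic model is the analysis planned for the co-morbidity objective. Without a rule written in advance, dropping a covariate or merging groups after a failed fit would be a data-driven choice in an open-label trial.

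**Working it through.** **1. Reproduce the sample size.** Inputs from section 12.3: p1 = 0.086, p2 = 0.015, two-sided alpha 0.05, power 0.85. With mean rate 0.0505 and difference 0.071:

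n = [1.960 × √(2 × 0.0505 × 0.9495) + 1.036 × √(0.086 × 0.914 + 0.015 × 0.985)]² / 0.071² = (0.607 + 0.317)² / 0.071² = 169.2, so 170 per arm.

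Continuity correction: (169.2/4) × [1 + √(1 + 4/(169.2 × 0.071))]² = 196.4, so 197 per arm and 394 in all. This matches the plan.

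**2. Expected events.** 197 × 0.086 = 16.9 and 197 × 0.015 = 3.0, total 19.9. At the accrual ceiling of 400 the total is 200 × 0.101 = 20.2.

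**3. Terms.** Treatment 1, co-morbidities 4, blood pressure 1, age 1, race 1 (two groups) to 3 (four groups; the coding is not given): 8 to 10 main effects. Events per term: 19.9/8 = 2.5 and 19.9/10 = 2.0.

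**4. No event on 162 mg.** 0.985^197 = 5.1%. None or one: 20.4%.

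**5. Precision.** The unadjusted log-OR standard error is √(1/16.9 + 1/180.1 + 1/3.0 + 1/194.0) = 0.64, and about 0.65 with adjustment. Around an OR of 0.157, the adjusted value corresponding to the two rates, 0.64 gives a 95% interval of about 0.04 to 0.55.

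**6. Simulation at 197 per arm and 8.6% vs 1.5%.** The documents give no co-morbidity prevalences or effects, so these are assumptions. Odds ratios were 1.5 for diabetes, 2 for chronic hypertension, 2 for renal and 1.5 for autoimmune disease, 1.4 and 1.1 per standard deviation of blood pressure and age, and 1.3 for each non-reference race group. There were 1,000 trials per setting.

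| Assumed prevalence (diabetes / hypertension / renal / autoimmune) | Trials with a non-estimable logistic term, 8 and 10 terms | Median OR (true 0.156-0.158) |
|---|---|---|
| 30 / 50 / 20 / 20% | 6% and 10% | 0.143, 0.146 |
| 25 / 40 / 8 / 10% | 19% and 21% | 0.138, 0.144 |
| 15 / 30 / 4 / 5% | 46% and 47% | 0.142, 0.140 |

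Other settings, with renal disease at 3-10% and autoimmune disease at 5-15%, gave 8-54%. The full range is therefore about 6-54%. For the Cox model a term was non-estimable in 18-22% of trials.

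**7. Size of the bias.** The geometric mean OR among usable fits was about 0.133 to 0.142. ln(0.133/0.157) = -0.17 and ln(0.142/0.157) = -0.10, which is 0.15 to 0.26 of a standard error of 0.65. About 20% of usable fits gave an OR below half the true value; most of that is sampling error. Average bias in the covariate log odds ratios was within about 0.05, so for the covariates the trouble is non-estimability.

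**8. Firth logistic fit on the same design.** Every fit was estimable, the average OR was 0.150 to 0.163, and interval coverage was 94-95%.

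**9. More events.** At 33.6% on 81 mg:

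- Same ratio of rates as planned: 197 × 0.336 × (1 + 0.015/0.086) = 78 events.
- Same 7.1-point difference (33.6% vs 26.5%): 197 × 0.601 = 118 events.
- No difference: 2 × 197 × 0.336 = 132 events.

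At 78 and 132 events, 0-1% of ten-term fits were non-estimable. At 118 events maximum likelihood gave 0.682 and Firth 0.691, against a true 0.694.

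**10. Interactions.** Treatment by each of 9 covariate terms makes 10 + 9 = 19 terms. At the design rates and moderate prevalence, 99% of maximum-likelihood fits were non-estimable.

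**The case against.** The strongest reply is that the plan does not rely on its own rates. Section 12.3 calls them approximate, sets 8.6% far below the local 33.6%, and re-estimates the sample size after stage 1. This stands, and it is why the point is conditional. It does not remove the point. The plan also regards 33.6% as inflated by referral and by a period before aspirin was routine, so the count is unknown between about 20 and 130. The re-estimation targets power for the observed difference between arms, not the events needed by the adjusted models.

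The count could also exceed 20 because section 12.5 models PE incidence, while section 2.1.3 describes the 150 mg trial's result as preterm delivery due to PE. If the 1.5% counts preterm disease only, all PE would be more frequent. This is fair, and another reason to state a range.

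A reader might infer that the adjusted models will fail, or will materially overstate the benefit of 162 mg. The documents do not support that. In most simulated settings the large majority of main-effects fits converge, and the average bias is a fraction of a standard error. The high failure rates depend on rare co-morbidities, and section 3.2 defines renal disease broadly (an eGFR below 90 suffices), so very low prevalence is not evident.

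A reader might also infer that the trial's main conclusion is at risk. It is not: the primary test is unadjusted, and these analyses are secondary or exploratory.

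Finally, fewer covariates, or a rule triggered by the event count, would also deal with sparse data. That is true. Firth estimation keeps the covariate list and needs no decision after the data are seen.

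**Conclusion.** The point holds in conditional form, as a cheap improvement of minor severity. If events are near the sizing assumption, the adjusted models have 2.0 to 2.5 events per term. Ordinary fits then carry roughly a 6-54% chance of at least one non-estimable coefficient and a 5.1% chance of an estimated treatment OR of 0, and the treatment OR is modestly exaggerated. Near 80-130 events main-effects models are essentially sound.

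The event counts, the term count and the 5.1% follow from the plan's figures, given main effects only and two to four race groups. The failure rates and the bias rest on assumed prevalences and effects. The main-effects reading is the lenient one: sections 12.4 and 12.5 speak of how the covariates bear on the treatment-outcome relationship, which may mean interactions. If so, and if all are fitted in one model at about 20 events, almost every maximum-likelihood fit would be non-estimable.

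**What to change.** In section 12.5:

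1. Fit the adjusted logistic model by Firth penalised likelihood with profile penalised-likelihood confidence intervals, and apply the same penalty to the adjusted Cox model. Adopting it regardless of the final count avoids a post-hoc switch, and at 118 events it made no material difference. The penalised fit was checked by simulation for the logistic model; for the Cox model the recommendation rests on the same reasoning.
2. State the expected range of PE events, about 20 to 130, beside the covariate list, and give the coding of race and blood pressure.
3. Say whether treatment-by-covariate interactions are intended. If they are, do not fit them all in one model when events are near 20.

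The cost is SAP wording and a user-written routine in place of the built-in Stata commands, with slight shrinkage and less familiar output. No extra patients or data are needed.

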#### **3.2 Inclusion Criteria**

Major Inclusion Criteria:

Pregnant patients,  $\geq 18$  years old, at less than 16 weeks' gestation (as documented by ultrasound) with at least one of the following risk factors for developing PE:

- PE in a prior pregnancy
- Chronic hypertension (prior to pregnancy or before 20 weeks' gestation)
- Type 1 or 2 diabetes
- Renal disease (proteinuria  $\geq 300$ mg/day or estimated GFR $<90$ mL/min/1.73 m^2)
- Multifetal gestation
- Autoimmune disease (e.g. systemic lupus erythematosus, antiphospholipid syndrome)

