#### **12.4 Stratification Factors**

A secondary objective of this study is to assess the impact of specific co-morbidities (diabetes, chronic hypertension, renal disease and autoimmune disease), blood pressure control, age and race on the relationship between treatment group and PE incidence.

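### Prior PE and multifetal gestation qualify women for the trial but are left out of the adjusted models, which distorts the four co-morbidity estimates and leaves two enrolled groups unexamined

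*Combined protocol and SAP*

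**What the plan says.** Section 3.2 enrols pregnant women "with at least one of the following risk factors for developing PE" and lists six. Two of the six are "PE in a prior pregnancy" and "Multifetal gestation". The study population row of the Protocol Summary gives the same six: "preeclampsia in a prior pregnancy, multifetal gestation, chronic hypertension, Type 1 or 2 diabetes, renal disease, autoimmune disease".

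The analysis text uses a shorter list. Section 12.4, although headed as stratification factors, only restates an objective about "specific co-morbidities (diabetes, chronic hypertension, renal disease and autoimmune disease), blood pressure control, age and race". The exploratory objective in the Protocol Summary and in section 1 names the same four conditions. In section 12.5 the multivariable logistic regression assesses "co-morbidities (diabetes, chronic hypertension, renal disease and autoimmune disease), blood pressure, age and race on the relationship between treatment group and PE incidence", and time to PE is analysed with a log-rank test and "a cox-regression model to adjust for the above-mentioned possible confounders", which is the same list by reference.

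Sections 5.2 and 12.1 describe randomisation through REDCap and name no stratification variable. The primary outcome is tested by an unadjusted chi-square (section 12.5).

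**The concern.** Section 2.1.1 of the Background (on risk reduction with low-dose aspirin) names a history of PE and multifetal gestation among the conditions that raise PE risk. Both are grounds for entry, yet no model, stratum or subgroup mentions either, and no reason is given.

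Two things are at stake. First, the entry rule ties the omitted factors to the modelled ones. A woman who lacks all four modelled conditions can be in the trial only because she has prior PE, multifetal gestation or both. The models therefore compare women who have a named condition with women in whom the two omitted risk factors are over-represented, and the named condition can look less important than it is. Second, the plan wants to know whether patient characteristics alter the relationship between dose and PE, and two of the six enrolled groups are left out of that question.

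**Working it through.** **1. The lists side by side.**

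| Condition | Section 3.2 and summary population | Exploratory objective, 12.4, logistic and Cox models |
|---|---|---|
| Chronic hypertension | yes | yes |
| Type 1 or 2 diabetes | yes | yes |
| Renal disease | yes | yes |
| Autoimmune disease | yes | yes |
| Prior PE | yes | no |
| Multifetal gestation | yes | no |

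Six conditions qualify a woman, four are modelled and two are omitted.

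**2. What the entry rule does.** The documents give no prevalences, so the following are assumptions, taken as independent before entry: prior PE 30%, multifetal 15%, diabetes 25%, hypertension 40%, renal 8%, autoimmune 10%.

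- None of the four modelled conditions: 0.75 × 0.60 × 0.92 × 0.90 = 0.373.
- Prior PE and/or multifetal: 1 − 0.70 × 0.85 = 0.405.
- Eligible (at least one of six): 1 − 0.373 × 0.595 = 0.778.
- Share of enrolled women with none of the four: 0.373 × 0.405 / 0.778 = 0.19. All of them have an omitted factor.
- Share of women with an omitted factor who also have a modelled condition: 1 − 0.373 = 0.63.
- Among enrolled women with hypertension, 40.5% have an omitted factor. Among those without it, the share is 0.405 / (1 − 0.75 × 0.92 × 0.90 × 0.595) = 0.405 / 0.631 = 64%.

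Conditions that were independent before entry are thus negatively associated among participants.

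**3. Effect on the logistic model.** Outcomes were simulated for 400,000 eligible women with the prevalences above. The assumed true odds ratios were treatment 0.6, hypertension 2.0, diabetes 1.8, renal 1.8 and autoimmune 1.5. Each omitted factor was given an odds ratio of 1.5, 2.5 or 4. The last four columns show the four-condition model.

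| OR of each omitted factor | PE rate | Hypertension (true 2.0) | Diabetes (true 1.8) | Renal (true 1.8) | Treatment (true 0.6) |
|---|---|---|---|---|---|
| 1.5 | 13.3% | 1.77 | 1.70 | 1.71 | 0.61 |
| 2.5 | 17.5% | 1.55 | 1.48 | 1.55 | 0.60 |
| 4 | 22.7% | 1.33 | 1.32 | 1.34 | 0.64 |

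The six-condition model recovers hypertension at 1.97 to 2.01, diabetes at 1.80 to 1.83 and treatment at 0.59 to 0.61. With a sample this large the attenuation is not noise, so recruiting more women would not remove it. The Cox model was not simulated, but the same association among covariates applies there.

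**4. Events available for more terms.** The plan's 197 per arm is reproduced for 8.6% vs 1.5%, 85% power and two-sided 5%, using the pooled two-proportion formula with continuity correction (170 per arm without it). At those rates the expected events are 197 × 0.086 + 197 × 0.015 = 16.9 + 3.0, about 20. At the 33.6% site rate in section 12.3 they are 394 × 0.336 = 132.

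Treatment, four conditions, blood pressure, age and race need at least 8 parameters, and two more make 10. Events per parameter would fall from 20/8 = 2.5 to 20/10 = 2.0 at the planning rates, or from 132/8 = 16.5 to 132/10 = 13.2 at the site rate.

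**The case against.** The strongest reply is that the four-item list may be deliberate. The objective speaks of specific co-morbidities and then names them. Prior PE is obstetric history and multifetal gestation is a feature of the current pregnancy, so neither is a co-morbidity in the usual sense, and the models match the objective as written. That is a possible reading, but the protocol does not give it as a reason. It also does not answer the estimation problem, because the four named effects are themselves distorted by the omission.

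The second reply is that the main result is safe. This stands in full: the primary chi-square and the log-rank test are unadjusted comparisons of randomised arms.

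Three stronger readings are tempting and are not supported.

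- A reader might infer that chance imbalance in the omitted factors biases the dose comparison. For a factor held by 15% of women, the 95% range of the between-arm difference is 1.96 × √(2 × 0.15 × 0.85/197), about ±7.1 points. Multiplied by an assumed 15-point effect on risk, that gives about 1 point. This is chance variation, already covered by the test's error rate. The assumed effect also does not fit the plan: it alone would contribute 0.15 × 15 = 2.25 points, more than the 1.5% expected in the higher-dose arm.
- A reader might infer that the co-morbidity contrasts have no interpretable reference. Each coefficient compares women with and without that condition given the other terms, not with the all-zero group alone. In the illustration that group is only 19% of participants, and 63% of women with an omitted factor lie outside it.
- A reader might infer that the two factors will never be looked at. Section 12.5 compares baseline characteristics across arms and section 5.1 collects medical history at baseline, so both could be tabulated, although neither is named.

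The objection that extra terms cost precision also stands, and it shapes the fix.

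**Conclusion.** The point holds for the adjusted secondary and exploratory analyses only. That two of six qualifying risk factors are missing from the logistic and Cox models is a matter of text and needs no assumption. So is the fact that every woman with none of the four modelled conditions has at least one of the two omitted ones.

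The size of the distortion does rest on assumptions: the prevalences, the odds ratios and independence of the conditions before entry. Under these, a hypertension odds ratio of 2.0 falls to between 1.77 and 1.33 and a diabetes odds ratio of 1.8 to between 1.70 and 1.32. If an omitted factor and a modelled one tend to occur together in the source population, the attenuation would be smaller or could be offset. The treatment odds ratio moves little (0.60 to 0.64 against 0.6), and the primary conclusion is not threatened. The question of whether the dose effect varies remains unasked for women with prior PE and for women with multifetal gestation. The change should be made, but it does not affect the sample size or the primary test.

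**What to change.** In section 12.5, add prior PE and multifetal gestation as separate baseline yes/no covariates, alongside the four named conditions, in both the logistic and the Cox model. Allow more than one condition per woman. Align the lists in the Protocol Summary, the exploratory objective in section 1 and section 12.4. This edits a stated objective, so it is a protocol change and not only an analysis detail. If the sponsor prefers the four-item list, the plan should say why.

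Show the dose comparison in all six groups as counts and estimates with intervals. Label it descriptive and note that the groups overlap. At the planning rates about three events are expected in the higher-dose arm, so these tables cannot support formal subgroup claims.

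No new data are needed, because both factors must be ascertained for eligibility. The cost is two more model terms, or four if treatment interactions are fitted. If events turn out near 20, specify in advance a penalised fit (for example Firth) or a smaller covariate set that keeps these two factors. The plan should also check how many women have more than one condition. If nearly all had exactly one, the six indicators would sum to one and could not be separated from the intercept; the conditions would then have to be reported as contrasts between groups.
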